3.2. Primary Analyses

The planned primary analyses will be performed after the completion of the following sequential steps:

1. The study reaches 6 months after the last participant in frozen liquid configuration is randomized in the study.
2. All required database cleaning activities have been completed and database release (DBR) and database freeze (DBF) have been declared by Data Management.
3. All criteria for unblinding the randomization codes have been met.
4. Randomization codes have been distributed according to RandAll NG.

An updated analysis for OS will be performed at end of study as defined in Section 4.6 of protocol (Version: GSK Document Number [TMF-13990464](#)).

4. ANALYSIS POPULATIONS

Population		Definition / Criteria	Analyses Evaluated
All Screened		
 • All participants who sign the ICF to participate in the study. 	
 • Study Population
Enrolled		
 • All participants who passed screening. Note screening failures (who never passed screening even if rescreened) and participants screened but never enrolled into the study (Reserve, Not Used) are excluded from the Enrolled population as they did not enter the study. Same participant enrolled more than once will be counted only once based on the last randomization number. • This population will be based on the treatment the participant was randomized to. 	
 • Study Population
Frozen liquid configuration	Intent-to-Treat (ITT)	
 • All randomized participants whether or not randomized treatment was administered. • This population will be based on the treatment the participant was randomized to. • Any participant who receives a treatment randomization number will be considered to have been randomized. Same participant receiving multiple randomization numbers will be counted only once using the last randomization number. 	
 • Study Population • Efficacy • EORTC QLQ-C30 and EORTC QLQ-MY20
	Efficacy	
 • Efficacy population will consist of first 130 ITT participants whether or not randomized treatment was administered. This population will be based on the treatment to which the participant was randomized and will be used for sensitivity analysis of 	
 • Selected efficacy

Population		Definition / Criteria	Analyses Evaluated
		primary and selected secondary efficacy endpoints.	
	Evaluable	
 All participants who have at least two doses of study treatment and have completed at least one disease assessment after the second dose, or progressed or died or discontinued treatment due to other reasons. 	
 Futility analyses at IA
	Safety	
 All randomized participants who received at least one dose of Frozen liquid study treatment. This population will be based on the treatment the subject actually received (first dose). 	
 Safety PRO-CTCAE, NEI-VFQ-25 and OSDI.
	Ocular Sub-Study	
 All randomized participants to ocular sub-study who received at least one dose of study treatment. This population will be used to evaluate the effect of topical corticosteroids on corneal events/findings in approximately 30 participants who will receive monocular topical corticosteroids for the first 4 cycles 	
 Corneal events/findings
Lyophilized configuration	Lyo	
 All randomized participants who receive at least 1 dose of lyophilized study treatment. 	
 All analysis other than PK
Full Analysis		
 All participants included in either ITT or Lyo population This population will be based on the treatment the participant was randomized to 	
 Study population Efficacy EORTC QLQ-C30 and EORTC QLQ-MY20
Full Safety		
 All participants who receive at least 1 dose of study treatment (frozen liquid or lyophilized). This population will be based on the treatment the subject actually received (first dose). 	
 Safety PRO-CTCAE, NEI-VFQ-25 and OSDI.
Full Pharmacokinetic (PK)		
 All participants in the Full Safety population who had at least 1 non-missing PK assessment (Non-quantifiable [NQ] values will be considered as non-missing values). 	
 PK

Note: Refer to [Appendix 13: List of Data Displays](#) which details the population used for each display being generated in the final version of the RAP.

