7. EFFICACY ANALYSES

The efficacy analyses will be based on the ‘Intent-to-Treat’ or ‘Efficacy’ population for frozen liquid cohort alone, and ‘Full Analysis’ population for frozen liquid cohort plus lyophilized cohort (side-by-side presentation). If needed, the efficacy analyses for lyophilized cohort alone will be based on the ‘Lyo’ population.

Unless otherwise specified, no ‘Total’ column will be provided for efficacy outputs

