7.1.3. Population of Interest

ORR at primary analysis will be analyzed using both ITT and Efficacy population for frozen liquid cohort, and Lyo population for lyophilized cohort.

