7.2.3. Population of Interest

For frozen liquid cohort, CBR, TTR, and DoR will be analyzed using both ITT and Efficacy population, and other TTE endpoints will be analyzed using ITT population only.

For lyophilized cohort, all secondary efficacy endpoints will be analyzed using Lyo population.

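### Full Analysis joins an all-randomized frozen-liquid set to a dosed-only lyophilized set, so the side-by-side ORR and CBR use a more lenient denominator for the lyophilized cohort if anyone assigned to it was never dosed

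*SAP*

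**What the plan says.** SAP Section 4 sets out three definitions that meet in the same tables.

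- **ITT**, listed under the frozen liquid configuration: "All randomized participants whether or not randomized treatment was administered".
- **Lyo**, listed under the lyophilized configuration and used for everything except PK: "All randomized participants who receive at least 1 dose of lyophilized study treatment".
- **Full Analysis**: "All participants included in either ITT or Lyo population", with the added statement "This population will be based on the treatment the participant was randomized to".

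Section 7 names Full Analysis as the population for presenting the frozen and lyophilized cohorts side by side. Section 7.1.3 states: "ORR at primary analysis will be analyzed using both ITT and Efficacy population for frozen liquid cohort, and Lyo population for lyophilized cohort". Section 7.2.3 adds: "For lyophilized cohort, all secondary efficacy endpoints will be analyzed using Lyo population". Appendix 13 assigns Full Analysis to Tables 2.0010 (IRC best response), 2.0060 (duration of response), 2.0080 (PFS), 2.0100 (TTP) and 2.0150 (OS), and to the disposition Tables 1.0010 and 1.0020.

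Section 7.1.1 counts only assessments made from the start of treatment, and it keeps participants with missing or non-evaluable responses in the denominator as non-responders.

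**The concern.** The frozen arms have two sets: an all-randomized one for efficacy and a dosed one for safety. The lyophilized cohort has a single dosed-only set for both purposes. Full Analysis carries that difference into one table, under a label saying that it follows randomized treatment. Nothing in its definition warns that the columns have different entry rules.

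A never-dosed participant has no assessment after the start of treatment and so cannot be a responder. In a frozen column that person lowers the ORR and CBR; in the lyophilized column the person is absent. Efficacy of the lyophilized configuration is a stated exploratory objective (Section 2.2), and readers will naturally look across to the 3.4 mg/kg frozen column if the lyophilized cohort is treated at that dose. The lyophilized cohort is already a separate single-dose group, and a difference in entry rule adds an avoidable obstacle to that reading. Withdrawals before first dose would also be missing from the lyophilized columns of the two disposition tables.

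**Working it through.** **Figures stated in the plan.** The SAP gives no response figure for the lyophilized cohort. Its only related figures, in Table 1 of Section 3.1.1, concern the frozen arms. They were checked with the exact two-stage binomial, the sum over x = 5 to 25 of P(X1 = x; 25, p) × P(X2 ≥ r − x; n − 25, p):

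| Boundary | p = 15% | p = 33% |
|---|---|---|
| Interim, ≤4 of 25 | 68.21% | 4.96% |
| Final, ≥17 of 65 | 1.23% | 88.00% |
| Final, ≥24 of 100 | 0.97% | 93.70% |

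All agree with Table 1. None depends on how the lyophilized cohort is counted.

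**Who is in which column**

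| Participant | Frozen column | Lyophilized column |
|---|---|---|
| Assigned and dosed | included | included |
| Assigned, never dosed | included; ORR non-responder | excluded |

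**Inputs for ORR.** The lyophilized cohort is about 25 participants (Section 2.2); 25 dosed is taken here. The number of responders x and the number never dosed k are not in the SAP. Both are assumptions: x = 4, 8 or 13, and k = 0 to 3.

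**Formulas.** Dosed-only ORR = x/25. ORR under the frozen rule = x/(25 + k). Overstatement = x/25 − x/(25 + k) = xk/[25(25 + k)]. For x = 8 and k = 3 this is 24/700 = 3.4 points.

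| x | k = 0 | k = 1 | k = 2 | k = 3 |
|---|---|---|---|---|
| 4 | 16.0% | 15.4% | 14.8% | 14.3% |
| 8 | 32.0% | 30.8% | 29.6% | 28.6% |
| 13 | 52.0% | 50.0% | 48.1% | 46.4% |

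The overstatement is zero at k = 0 and runs from 0.6 points (x = 4, k = 1) to 5.6 points (x = 13, k = 3). For x = 8, the exact 97.5% interval is 13.2% to 56.3% at k = 0 and 11.7% to 51.3% at k = 3, so the shift is small against the uncertainty. CBR is a proportion with the same denominator rule and moves in the same direction.

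**Other endpoints, from the SAP's own rules**

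- *DoR* (Section 7.2.1.3) covers responders only. A never-dosed participant is never among them, so the estimates do not change.
- *PFS and TTP* (Tables 4 and 5): a living participant with no post-baseline assessment is censored at randomization and adds nothing to later risk sets. What remains is early death. For PFS that means any death without an extended gap; for TTP, a death due to progression counts as the event.
- *OS* (Section 7.2.1.7) runs from randomization. A death before dosing would add an event, long follow-up alive would add survival time, and a withdrawal would be censored at that date. The curve could move either way.
- *Disposition*: Tables 1.0010 and 1.0020 omit these participants. Table 1.0070 (study populations) and Listing 1.0070 (exclusions from any population) use the Enrolled population, so they still show them.

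**The case against.** The strongest case on the other side is that the populations are stated openly, the lyophilized cohort is an independent single-dose group, its efficacy is descriptive, and no contrast with the frozen arms is planned. An all-randomized set mainly protects a randomized comparison, and this is not one. The Kaplan-Meier figures for DoR, PFS, TTP and OS and the ORR forest plots in Appendix 13 use ITT or Efficacy, so they do not mix the cohorts. The SAP is also at its second amendment, dated April 2022, after the primary analysis, and redefining a population now would separate the end-of-study tables from the earlier delivery. All of this stands, and it limits the weight of the point. It does not make the denominators in one table alike.

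One might also argue that ITT, by counting anyone who receives a randomization number, already takes in never-dosed lyophilized participants. The frozen-liquid row heading, the use of ITT for the frozen cohort alone in Sections 6.1 and 7, and the wording of Sections 7.1.3 and 7.2.3 rule that out.

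A reader might infer more than the document supports:

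- *That every lyophilized efficacy estimate is biased upward.* Only ORR and CBR have a fixed direction, and only if someone was never dosed and there is at least one responder.
- *That pre-dose withdrawals vanish from the report.* They remain in the Enrolled-based summary and listing.
- *That the primary conclusion is at risk.* It rests on the frozen arms alone.

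**Conclusion.** The inconsistency in definitions is real, and its consequence is minor. As written, the lyophilized ORR and CBR have a more lenient denominator than the frozen columns beside them, and Tables 1.0010 and 1.0020 leave out never-dosed lyophilized participants. With 25 dosed and 8 responders, the ORR overstatement is 1.2, 2.4 or 3.4 points for 1, 2 or 3 never dosed. Both the responder count and the number never dosed are assumed, and if everyone assigned was dosed the effect is nil. The lyophilized column size of 25 in mock shell SAFE_T22 does not settle this, because that shell is for the Full Safety population and does not show how many were assigned. The frozen-arm hypothesis test, type I error and power do not change.

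**What to change.** For the side-by-side efficacy and disposition tables, define Full Analysis as all participants assigned a treatment number in either configuration, whether or not dosed. Keep the dosed-only Lyo set for safety. Sections 7.1.3 and 7.2.3 would need matching wording. Section 8 should point its side-by-side safety displays to Full Safety, as Section 4 and Appendix 13 already do; its text currently names Full Analysis.

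If lyophilized efficacy is to stay dosed-only, show the 3.4 mg/kg frozen column on the dosed population as well in the same display, and report the number assigned to the lyophilized cohort but never dosed.

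The cost is one population flag and some SAP wording, and the ITT frozen-arm results do not change. The lyophilized ORR may be slightly lower, and the end-of-study tables may need a note explaining the change from the primary-analysis tables.

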4.1. Protocol Deviations

Important protocol deviations (including deviations related to study inclusion/exclusion criteria, conduct of the trial, patient management or patient assessment) will be summarised and listed.

Protocol deviations will be tracked by the study team throughout the conduct of the study in accordance with the Protocol Deviation Management Plan [Version 4.0, dated 22Mar2022].

- Data will be reviewed prior to freezing the database to ensure all important deviations are captured and categorised on the protocol deviations dataset.
- This dataset will be the basis for the summaries and listings of protocol deviations.

A separate summary and listing of all inclusion/exclusion criteria deviations will also be provided. This summary will be based on data as recorded on the inclusion/exclusion page of the eCRF.

5. CONSIDERATIONS FOR DATA ANALYSES AND DATA HANDLING CONVENTIONS

5.1. Study Treatment & Sub-group Display Descriptors

Treatment Group Descriptions			
RandAll NG		Data Displays for Reporting	
Code	Description	Description	Order in TLF
B	2.5 mg/kg frozen liquid solution of GSK2857916	2.5 mg/kg	1
A	3.4 mg/kg frozen liquid solution of GSK2857916	3.4 mg/kg	2
C	lyophilized configuration of GSK2857916	3.4 mg/kg Lyo, actual dose level subject to IA result	3
L	receive topical corticosteroids in left eye only	"3.4 mg/kg treated eye" for the treated eyes of participants in 3.4 mg/kg group (frozen liquid);	4
		"3.4 mg/kg untreated eye" for the untreated eyes of participants in 3.4 mg/kg group (frozen liquid)	5
R	receive topical corticosteroids in right eye only	"2.5 mg/kg treated eye" for the treated eyes of participants in 2.5 mg/kg group (frozen liquid);	6
		"2.5 mg/kg untreated eye" for the untreated eyes of participants in 2.5 mg/kg group (frozen liquid).	7

5.2. Baseline Definitions

For all endpoints (except as noted in baseline definitions) the baseline value will be the latest pre-dose assessment with a non-missing value, including those from unscheduled visits. If time is not collected, Day 1 assessments are assumed to be taken prior to first dose and used as baseline. For subjects who did not receive study treatment during the study, baseline will be defined as the latest, non-missing collected value.

For laboratory data, baseline will be the latest non-missing pre-dose value from central lab. If no central lab value is available, the latest non-missing pre-dose value from local lab will be used.

For ECG analyses, subject level baseline is defined as the mean of triplicate baseline assessments.

Unless otherwise stated, if baseline data is missing, no derivation will be performed, and baseline will be set to missing.

5.3. Examination of Covariates, Other Strata and Subgroups

5.3.1. Covariates and Other Strata

The list of strata may be used in descriptive summaries and statistical analyses, some of which may also be used for subgroup analyses. Additional strata of clinical interest may also be considered.

Category	Details
Number of prior lines of therapy	≤4, >4
Cytogenetic risk	high risk, Other (non-high risk - all others)

NOTES: A subject is considered as high risk if the subject has any of the following cytogenetics: t(4;14), t(14;16), and 17p13del.

5.3.2. Examination of Subgroups

The list of subgroups may be used in descriptive summaries and statistical analyses. Additional subgroups of clinical interest may also be considered.

- If the percentage of subjects is small within a particular subgroup, then the subgroup categories may be refined prior to unblinding the trial.

Subgroup	Categories
Age Group (at screening)	18 to <65, 65 to < 75, ≥ 75
Sex	Male, Female
Ethnic Background	White, Black, Other
ISS Staging at Screening	I, II, III, Other (Unknown or Missing)
Baseline renal impairment status per eGFR (ml/min/1.73 m ²)	Normal (≥ 90), Mild (≥ 60, < 90), Moderate (≥ 30, < 60), Severe (≥ 15, < 30)
Number of prior lines of therapy	<=4, >4
Type of myeloma	IgG, Non-IgG
Cytogenetics Risk ^[1]	High, Other (non-high risk - all others)
Refractory to prior anti-cancer therapy	Any Proteasome Inhibitor (PI) Bortezomib Carfilzomib Ixazomib Any Immunomodulator (IMiD) Thalidomide Lenalidomide Pomalidomide Any Monoclonal Antibodies Elotuzumab Isatuximab Daratumumab Daratumumab alone ^[2]

Subgroup	Categories
	Daratumumab in combination ^[3] PI+IMiD Daratumumab+PI+IMiD Penta-refractory ^[4]

NOTES:

^[1] A subject is considered as high risk if the subject has any of the following cytogenetics: t(4;14), t(14;16), and 17p13del.

^[2] Defined as prior CTX regimen with Daratumumab as the only drug in the regimen.

^[3] Defined as prior CTX regimen with Daratumumab and other drugs.

^[4] Defined as refractory to: Bortezomib, AND Carfilzomib AND Lenalidomide AND Pomalidomide AND Daratumumab.

5.4. Other Considerations for Data Analyses and Data Handling Conventions

Other considerations for data analyses and data handling conventions are outlined in the appendices:

Section	Component
Section 15.3	Appendix 3: Assessment Windows
Section 15.4	Appendix 4: Study Phases and Treatment Emergent Adverse Events
Section 15.5	Appendix 5: Data Display Standards & Handling Conventions
Section 15.6	Appendix 6: Derived and Transformed Data
Section 15.7	Appendix 7: Reporting Standards for Missing Data
Section 15.8	Appendix 8: Values of Potential Clinical Importance

6. STUDY POPULATION ANALYSES

6.1. Overview of Planned Study Population Analyses

The study population analyses will be based on the “Intent-to-Treat” population for frozen liquid cohort alone, and ‘Full Analysis’ population for frozen liquid cohort plus lyophilized cohort (side-by-side presentation). If needed, the study population analyses for lyophilized cohort alone will be based on the “Lyo” population.

Unless otherwise specified, no ‘Total’ column will be provided for study population outputs.

Study population analyses including analyses of subject’s disposition, protocol deviations, demographic and baseline characteristics, prior and concomitant medications, subsequent anti-cancer therapy, and exposure and treatment compliance will be based on GSK Core Data Standards. Details of the planned displays are presented in [Appendix 13: List of Data Displays](#).

6.2. Disposition of Subjects

A summary of the number of subjects in each of the analysis populations described in Section 4 will be provided (for primary analysis, Evaluable population will not be included). In addition, the number of subjects enrolled by centre will be summarized by dose level using the “Enrolled” population. A separate summary for exclusions from each study population will be displayed (for primary analysis, Evaluable population will not be included). A listing of subjects excluded from analysis populations will also be provided.

A summary of subject status and reason for study withdrawal will be provided. This display will show the number and percentage of subjects who withdrew from the study, including primary reasons for study withdrawal. Reasons for study withdrawal will be presented in the order they are displayed in the eCRF.

A summary of study treatment status will be provided. This display will show the number and percentage of subjects who are ongoing or discontinued study treatment and a summary of the primary reasons for discontinuation of study treatment. Reasons for study treatment discontinuation will be presented in the order they are displayed in the eCRF. A listing of study treatment discontinuation will be generated. The listing will include last dose date, and reasons for study treatment discontinuation.

A listing of subjects with visits and assessments Impacted by the COVID-19 Pandemic will be presented. A stacked bar chart depicting visits impacted by COVID-19 will be presented.

6.3. Demographic and Baseline Characteristics

The demographic characteristics (e.g., age, race, ethnicity, sex, baseline height, and baseline body weight and baseline BMI) will be summarized and listed. Age, height,

weight and BMI will be summarized using the mean, standard deviation, minimum, median, and maximum. The count and percentage will be computed for sex and ethnicity.

Race and racial combinations will be summarized and listed.

Disease history and characteristics (e.g. time since initial diagnosis in years, stage at initial diagnosis, date of initial diagnosis) at initial diagnosis and screening will be listed. Separate summaries of disease characteristics at initial diagnosis and screening will be provided. Disease characteristics at screening, including stage, type of multiple myeloma, number of prior lines, and types of therapy, myeloma light chain and myeloma immunoglobulin, extramedullary disease, lytic bone lesion, and genetic characteristics (including high cytogenetic risk) will be summarized and listed.

Medical conditions collected at screening will be listed and will be summarized by past and current and by cancer-related and non-cancer related categories.

Substance use, including smoking history and alcohol use will be summarized.

Prior anti-cancer therapy will be coded using GSK Drug coding dictionary, then summarized by type of therapy and listed. A listing of prior anti-cancer therapy will show the relationship between ATC Level 1, Ingredient, and verbatim text. A summary of the best response to the most recent prior anti-cancer therapy will be provided. A summary of the number of prior anti-cancer therapy regimens will also be produced.

Prior anti-cancer therapy for multiple myeloma subjects will also be summarized by type of therapy, and drug class. A summary of multiple myeloma subjects' refractory to prior anti-cancer therapy by drug class will be provided.

Anti-cancer radiotherapy will be listed. Prior cancer and non-cancer related surgeries will be summarized. Prior and on treatment cancer and non-cancer related surgeries will be listed.

6.4. Treatment Compliance

Summaries of study treatment exposure and dose modifications (e.g., number of dose reductions, number of dose delays) will further characterize compliance. These analyses are described in Section 6.5 'Extent of Exposure'.

6.5. Extent of Exposure

Extent of exposure to GSK2857916 will be summarized.

The number of cycles administered to study treatment will be summarised with mean, median, standard deviation, minimum, and maximum.

Dose delivered per cycle (mg/kg/cycle) will be summarized using mean, median, standard deviation, minimum, and maximum by cycle and overall. The dose intensity (mg/kg/3 weeks), which is calculated as the cumulative actual dose (mg/kg) divided by expected duration of exposure in 3 weeks (last infusion date – first infusion date +

21)/21), will also be summarized. A by subject summary listing of data on exposure to all study treatments will be produced.

Dose reductions will be summarised by number of reductions and reasons for reductions. Dose delays will be summarised by number of delays, reasons for the delays, and delay duration (days). The number and percentage of the delays for intervals of 1-21, 22-42 and >42 days will be computed. Primary reasons for dose reductions and dose delays will also be summarized by cycle. Listing of all dose delays due to corneal events (GSK scale) and listing of dose delays and associated Eye Disorder Events (CTCAE) will be produced.

Duration of delays is defined as period from the expected start date of dose to actual start date of current dose. Calculation: (actual start date of current dose - expected start date of dose). Expected start date of dose = actual start date of previous dose + 21.

The summaries of dose modifications will be provided. All the dose reductions, dose escalations, infusion interruptions, incomplete infusions and dose delays will be listed. A plot showing the number and percentage of subjects treated at different dose levels over time will be provided.

The duration of exposure to study treatment (from first day to last day of treatment) will be calculated and summarized using mean, median, standard deviation, minimum, and maximum. A horizontal bar graph of duration of treatment will be produced that displays duration of treatment in months for each subject. Summary of duration of exposure by response category based on IRC will be presented.

A Kaplan Meier curve for time to treatment discontinuation by Response Category Based on IRC, and a Kaplan Meier curve for time to treatment discontinuation for subjects who have received at least 3 cycles of the study treatment will be presented.

Swim-lane Plot of duration of study treatment for responder based on Independent Reviewer-Assessed Response will be produced.

